frequently with other drugs, and occasionally on placebo and spontaneously. No cases of ARIA-E have been observed to date in trials of atabecestat, but they may be expected in all large amyloid-lowering trials of AD since they occur on placebo.

A 6-month Phase 2a safety study with atabecestat (54861911ALZ2002) in subjects who have early AD (predementia) was initiated in December 2014, and this study will be followed by a long-term extension study (54861911ALZ2004). Both studies will provide information on the safety of atabecestat in the target population. In study 54861911ALZ2002 the blood values of hepatic enzymes in some patients were increased, indicating potential for liver injury. Importantly, there were no symptoms clearly related to these elevations, and upon discontinuation of the drug, the liver enzyme values have decreased towards normal, and there were no lasting effects. The further investigation of this signal is continuing, but there is potential that atabecestat can cause injury to the liver and therefore more frequent monitoring of these liver tests has been included in this study. To date (17 March 2017), more than 200 subjects have received atabecestat or placebo in studies longer than 1 month of treatment. Eleven subjects (9 on active drug, 1 on placebo, 1 blinded) have experienced an elevation in liver enzymes  $>3 \times$  upper limit of normal (ULN) in these studies. None of these subjects had symptoms related to these elevations in liver enzymes. One of these subjects, participating in this Study 54861911ALZ2003, was the subject of a new safety report of drug-induced hepatotoxicity (based on biopsy results). The treatment assignment was unblinded and the subject was found to be on 25 mg atabecestat. As this subject's increase in ALT and AST were observed in Month 1, increased monitoring in the first 3 months of dosing has been introduced.

Based upon these cases, the protocol has been modified to include more frequent monitoring of serum chemistry and hematology (indicated in the Time and Events Schedule), guidelines for discontinuation of treatment due to abnormal liver enzymes (Section 10.2), and guidelines for evaluation and management of such cases (Attachment 3).

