### 10.2. Discontinuation of Study Treatment

If a subject's study treatment must be discontinued before the end of the treatment regimen, this will not result in automatic withdrawal of the subject from the study.

Subjects who discontinue study treatment prematurely will be asked to complete all regular study visits through the end of the study. To reduce burden on subjects and increase compliance, the focus will be on collecting primary and secondary clinical outcome measures and reducing other assessments in these subjects.

Subjects who meet the criteria for discontinuation of study treatment should have the event reported as an SAE and should follow the SAE reporting as outlined in Section 12.3.2.

A subject's study treatment will be discontinued if the investigator believes that for safety reasons (eg, AE) it is in the best interest of the subject.

For subjects during the first 3 months of treatment with study drug, treatment must be discontinued if any of the following occurs (for details see Attachment 3):

- ALT or AST  $>5 \times \text{ULN}$
- ALT or AST  $>3 \times \text{ULN}$  and total bilirubin  $>2 \times \text{ULN}$  or International Normalized Ratio (INR)  $>1.5$
- ALT or AST  $>3 \times \text{ULN}$  with the appearance of fatigue, nausea, vomiting, right upper quadrant pain or tenderness, fever, rash, and/or eosinophilia  $>5\%$

For subjects that have completed 3 months of treatment with study drug, treatment must be discontinued if any of the following occurs (for details see Attachment 3):

- ALT or AST  $>8 \times \text{ULN}$
- ALT or AST  $>5 \times \text{ULN}$  for more than 2 weeks
- ALT or AST  $>3 \times \text{ULN}$  and (total bilirubin  $>2 \times \text{ULN}$  or INR  $>1.5$ )
- ALT or AST  $>3 \times \text{ULN}$  with the appearance of fatigue, nausea, vomiting, right upper quadrant pain or tenderness, fever, rash, and/or eosinophilia ( $>5\%$ )

Note: Abnormal liver enzymes greater than  $3 \times \text{ULN}$  at any time during the treatment phase should be confirmed within 24-72 hours (See Attachment 3).

If the subject has a QTcF interval of >500 msec and/or QTcF increase versus baseline of >60 msec, confirmed upon repeat ECG, after consultation with the sponsor's medical monitor, treatment must be discontinued.

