## **Adverse Events**

The verbatim terms used in the eCRF by investigators to identify AEs will be coded using the Medical Dictionary for Regulatory Activities (MedDRA). All reported AEs with an onset during the double-blind treatment phase and AEs that have worsened in intensity since baseline (ie, treatment-emergent adverse events [TEAEs]) will be included in the analysis. For each TEAE, the percentage of subjects who experience at least 1 occurrence of the given event will be summarized by treatment group.

Summaries, listings, datasets, or subject narratives may be provided, as appropriate, for those subjects who die, who discontinue treatment due to an AE, or who experience a severe or serious AE.

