1. INTRODUCTION

This statistical analysis plan (SAP) contains definitions of analysis populations, derived variables and statistical methods for the analysis of efficacy and safety for study 54861911ALZ2003.

Screening, randomization, and dosing in this study was stopped on 17 May 2018. Randomized subjects were to continue in the double-blind treatment phase without treatment (as allowed by protocol) for approximately 3 to 6 months from cessation of dosing. This permitted continued safety monitoring of the subjects per protocol. The planned last-patient-out date is 17 September 2018, except for some subjects who may require further follow-up.

At the time of cessation of screening and randomization, 557 (34%) subjects of the planned 1650 had been randomized. The planned duration of treatment was 54 months. As of the time of cessation of dosing, no subject had more than 27 months of treatment and 447 had 12 months of treatment or less.

As a result of the significantly reduced sample size, the objectives of the study as stated in the protocol and in Section 1.1 below cannot be evaluated. Safety outcomes will be summarized with descriptive statistics. The planned interim analysis of CSF A β ₁₋₄₀ was performed but other planned interim analyses will not be performed. Between-group comparisons of selected efficacy outcomes will be performed. Other efficacy outcomes will be summarized with descriptive statistics

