4.4. Extent of Exposure

The number and percentage of subjects who receive study medication will be summarized by treatment group.

Study medication duration is defined as: $(\text{date of last dose of study medication} - \text{date of first dose of study medication}) + 1$.

Descriptive statistics for study medication duration (N, mean, SD, median, and range (minimum, maximum)) will be presented by treatment group for the safety analysis set. Subject-years of exposure are calculated as days of exposure/365.25. Subject-years will be presented by treatment group.

Duration of exposure will be summarized in the following duration categories by treatment group and presented graphically in a histogram:

- <6 months (<180 days)
- 6 months - <1 year (181 to <365 days)
- 1 year – <1.5 years (365 to <548 days)
- 1.5 years - <2 years (548 to <730 days)
- 2 years - <2.5 years (730 to <913 days)

Cumulative exposure (≥ 6 months, ≥ 1 year, ≥ 2 years) will also be summarized.

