6.1 Adverse Events

The verbatim terms used in the CRF by investigators to identify adverse events will be coded using the Medical Dictionary for Regulatory Activities (MedDRA). Any AE occurring on or after the date of the initial administration of study medication through the day of last dose plus 7 days is considered to be treatment emergent. If the event date is recorded as partial or completely missing, then the event will be considered to be treatment emergent unless it is known to be prior to the first administration of study medication based on a partial onset date or resolution date. All reported treatment-emergent adverse events will be included in the analysis. For each adverse event, the number and percentage of subjects who experience at least 1 occurrence of the given event will be summarized by treatment group. AEs in the off-treatment period are the AEs with onset more than 7 days after the last dosing.

Summary tables will be provided for:

- AEs
- AEs with a fatal outcome

- Serious AEs (SAEs)
- AEs leading to discontinuation of study medication (events with action taken of ‘drug withdrawn’)
- AEs leading to termination of study participation (events associated with a trial termination reason of ‘adverse event’)
- AEs by severity

AEs will also be summarized by age group, by gender, and by race. In addition to the summary tables, listings will be provided for subjects who:

- Died
- Had SAEs
- Had AEs leading to discontinuation of study medication or termination of study participation

The above listings will include events with onset during the screening phase.

Incidence of other treatment-emergent adverse events of special interest will be summarized. Hypopigmentation related and retinal related adverse events are identified by the investigator on the AE eCRF page and include:

- Hypopigmentation Related Adverse Events
 - Hair and skin hypopigmentation (events related to lighting hair, skin coloration, or iris coloration)
- Retinal Related Adverse Events
 - Retinal changes

Hepatic related treatment-emergent adverse events will also be summarized. Adverse events related to abnormal LFTs are defined as follows:

Events belonging to the MedDRA Drug Related Hepatic disorders SMQ – comprehensive search

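### The AE tables give only crude percentages in on- and off-treatment windows that are likely to differ in length by arm; rates per subject-year at risk should stand beside them

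*SAP*

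**What the plan says.** **Measure.** SAP 6.1 sets the summary as follows: "the number and percentage of subjects who experience at least 1 occurrence of the given event will be summarized by treatment group". Protocol 11.10 plans the same: "the percentage of subjects who experience at least 1 occurrence of the given event will be summarized by treatment group".

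**Windows.** Under SAP 6.1, "Any AE occurring on or after the date of the initial administration of study medication through the day of last dose plus 7 days" counts as treatment-emergent, and "AEs in the off-treatment period are the AEs with onset more than 7 days after the last dosing". SAP 6 asks for every safety summary in both periods. No end point, denominator or person-time is stated for the off-treatment period.

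**Stopping and follow-up.** Protocol 10.2 and Attachment 3 set ALT and AST thresholds at which treatment must stop, with stricter ones in the first 3 months. Protocol 12.3.4 names raised liver enzymes as an adverse drug reaction. Protocol 10.2 adds: "Subjects who discontinue study treatment prematurely will be asked to complete all regular study visits through the end of the study". For the end of dosing on 17 May 2018, SAP 1 says: "Randomized subjects were to continue in the double-blind treatment phase without treatment (as allowed by protocol) for approximately 3 to 6 months".

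**Exposure.** SAP 4.4 says: "Subject-years will be presented by treatment group". It defines duration as first to last dose. SAP 4.2 tabulates discontinuations and their reasons by group. SAP 6.1.1 plans Kaplan-Meier curves for the first ALT or AST above the upper limit of normal (ULN) and above 3 times ULN, censored at the end of treatment, and repeats them off treatment. None of this is carried into the AE tables.

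**The concern.** Randomization balances the calendar cut-off of 17 May 2018 across arms. It does not balance stopping that the drug itself causes. If more subjects on active drug stop early and remain under observation, that arm loses on-treatment time and gains off-treatment time. A percentage with no time in the denominator then understates on-drug risk and overstates off-drug risk in that arm. Equal risks can look different, and a real excess on drug can be hidden.

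SAP 1 says that the study objectives can no longer be evaluated and that safety will be summarized descriptively. The AE tables are therefore among the main outputs left, and readers will compare them across arms. A spurious excess off treatment could also be taken for a delayed or withdrawal effect.

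**Working it through.** **The plan's own figures.** The SAP gives no AE risk to reproduce. Its exposure figures do reproduce: 557/1650 = 33.8% randomized (SAP: 34%), and 447/557 = 80.3% with no more than 12 months of treatment (SAP 5.1.1: 80%).

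**Inputs from the documents.** Follow-up after dosing ended was about 3 to 6 months (SAP 1), and 4 months is used here. Early stoppers are asked to stay (Protocol 10.2).

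**Assumptions, not in the documents.**
- Time from first dose to the sponsor's cessation: T = 9 or 12 months.
- The same constant event rate in both arms: 0.2, 0.5 or 1.0 per subject-year.
- Early stopping: 5% on placebo against 15% or 30% on active.
- Everyone is followed to the end. The 7-day tail is ignored.

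**Formulas.** Let λ be the monthly event hazard, s the monthly stopping hazard, p the proportion stopped early, and F = 4 months. Then s = −ln(1 − p)/T.
- On treatment: P_on = λ/(λ+s) × [1 − exp(−(λ+s)T)].
- Off treatment: P_off = ∫₀ᵀ s·exp(−su)·[1 − exp(−λ(T−u+F))] du + exp(−sT)·[1 − exp(−λF)].

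**One case in full: T = 9, 0.5 per subject-year, 30% v 5%.** λ = 0.5/12 = 0.04167. s = −ln(0.70)/9 = 0.03963 on active and −ln(0.95)/9 = 0.00570 on placebo.
- P_on, active: 0.5125 × (1 − exp(−0.7317)) = 26.6%. Placebo: 0.8797 × (1 − exp(−0.4263)) = 30.5%. Ratio 0.87.
- P_off, active: 0.0906 + 0.70 × 0.1535 = 19.8%. Placebo: 0.0148 + 0.95 × 0.1535 = 16.1%. Ratio 1.23.
- Mean months on drug, (1 − exp(−sT))/s: 7.6 v 8.8. Mean months off drug, 13 minus that: 5.4 v 4.2.

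**All cases at 0.5 per subject-year (active v placebo).** In the month-2 rows every early stop falls at month 2, so P_on = p·P(2) + (1−p)·P(T) and P_off = p·P(T−2+F) + (1−p)·P(F), with P(t) = 1 − exp(−λt).

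| Early stops | T (months) | Stopping | On treatment | Ratio | Off treatment | Ratio |
|---|---|---|---|---|---|---|
| Constant | 9 | 15% v 5% | 29.0% v 30.5% | 0.950 | 17.5% v 16.1% | 1.091 |
| Constant | 9 | 30% v 5% | 26.6% v 30.5% | 0.871 | 19.8% v 16.1% | 1.233 |
| Constant | 12 | 15% v 5% | 36.6% v 38.4% | 0.951 | 18.1% v 16.3% | 1.115 |
| Constant | 12 | 30% v 5% | 33.6% v 38.4% | 0.874 | 21.1% v 16.3% | 1.295 |
| Month 2 | 9 | 15% v 5% | 27.8% v 30.1% | 0.923 | 18.6% v 16.4% | 1.130 |
| Month 2 | 9 | 30% v 5% | 24.3% v 30.1% | 0.807 | 21.8% v 16.4% | 1.326 |
| Month 2 | 12 | 15% v 5% | 34.6% v 37.8% | 0.917 | 19.7% v 16.8% | 1.172 |
| Month 2 | 12 | 30% v 5% | 29.9% v 37.8% | 0.793 | 24.0% v 16.8% | 1.429 |

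Across all three event rates, the ratios run from 0.866 to 0.955 on and 1.075 to 1.339 off treatment with constant stopping. With stops at month 2 they run from 0.786 to 0.926 and 1.106 to 1.501.

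**Hidden excess (T = 9, constant stopping).** Solving for equal on-treatment percentages, a true active-to-placebo rate ratio of 1.06 to 1.07 (15% stopping) or 1.17 to 1.21 (30%) would show as no difference.

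**With time at risk in the denominator.** Mean on-treatment time to first event or stop is P_on/λ. In the full case this is 0.266/0.04167 = 6.4 months on active and 0.305/0.04167 = 7.3 months on placebo. Both arms then give 50 per 100 subject-years, a ratio of 1.00.

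**The case against.** The case against runs as follows. AEs are purely descriptive here, no test or error rate depends on them, and percentages are what Protocol 11.10 promised. Discontinuations, duration and subject-years by arm will be in the report, so a reader can see an imbalance and form a rough on-drug rate. The main safety signal, ALT and AST, already has censored curves in both periods. A liver event that itself causes the stop is counted before on-drug time is lost, so that first event is not missed. A constant-hazard rate suits early liver events poorly: Protocol 1.4 describes one case with onset in Month 1, and a longer exposure would dilute such a rate.

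The evidence for arm-related stopping is also indirect. The Protocol reports that "Eleven subjects (9 on active drug, 1 on placebo, 1 blinded) have experienced an elevation in liver enzymes" above 3 times ULN, but these were pooled over studies longer than 1 month with more than 200 subjects, up to March 2017. Exceeding 3 times ULN does not by itself require stopping under Protocol 10.2.

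Much of this stands. The size is unknown, and the point is an improvement rather than the correction of an error. Three things do not stand. The subject-years of SAP 4.4 run from first to last dose, so they are not cut at the first event and leave out the 7 days in which events still count. No off-treatment person-time is planned, so no off-treatment rate can be formed. The Kaplan-Meier curves cover two laboratory thresholds, not SAEs, hepatic AEs, AEs of special interest or the other event clusters.

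**Conclusion.** The point holds as a matter of presentation. The on- and off-treatment windows depend on stopping, a documented drug reaction can cause stopping, and the AE tables ignore time. Under the stated assumptions the distortion is modest on treatment (crude ratio about 0.87 to 0.96, or 0.79 to 0.93 with stops at month 2). It is somewhat larger off treatment (1.07 to 1.34, or 1.11 to 1.50). At 15% against 5% with constant stopping the on-treatment effect is only about 5%.

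Two stronger readings are not supported:
- A reader might infer that the active arms did have less on-drug time. The documents give no stopping rates by arm; this is likely, not shown.
- A reader might set an early stopper with 6 months on and 12 off drug against a subject with 9 on and 4 off. At 0.3 per subject-year that gives 13.9% v 20.1% on drug (ratio 0.69) and 25.9% v 9.5% off drug (ratio 2.7). This compares individuals, not arms: total follow-up is 18 v 13 months, whereas randomization balances calendar time. With 13 months in both, off-drug time is 7 v 4 months, which gives 16.1% v 9.5% (ratio 1.69). Even that needs a gap of 6 v 9 months on drug, wider than the 7.6 v 8.8 months that 30% against 5% stopping produces at T = 9.

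**What to change.** In SAP 6.1, keep n (%) and add the number of subjects with a first event per 100 subject-years at risk, by treatment group and period, at least for all AEs, SAEs, hepatic AEs and AEs of special interest. Define time at risk as follows:
- **On treatment:** from first dose to the earliest of first event, last dose plus 7 days, or last contact.
- **Off treatment:** from last dose plus 8 days to the earlier of first event or last contact. State the off-treatment denominator as well.

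Do not reuse the SAP 4.4 subject-years unchanged, for the reasons given under the objection. Where the hazard is clearly not constant, as for early hepatic events, apply the Kaplan-Meier approach of SAP 6.1.1 to the AE instead.

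The cost is programming: time at risk has to be derived separately for each event type. No new data are needed. The rates assume a roughly constant hazard, which is why the percentages stay alongside.

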## **Adverse Events of Special Interest**

Lightening of hair, lightening of skin, and ophthalmologic adverse events are AESIs. Subjects with AESIs may be counted or listed.

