## 12.3. Procedures

### 12.3.1. All Adverse Events

All AEs and special reporting situations, whether serious or nonserious, will be reported from the time a signed and dated ICF is obtained until completion of the subject's last study-related procedure (which may include contact for follow-up of safety). SAEs, including those spontaneously reported to the investigator within 30 days after the last dose of study drug, must be reported using the Serious Adverse Event Form. The sponsor will evaluate any safety information that is spontaneously reported by an investigator beyond the time frame specified in the protocol.

Progression of symptoms associated with AD should not be recorded as an AE unless they are considered to be accelerated in the opinion of the investigator.

Adverse events of special interest ie, lightening of skin, lightening of hair and ophthalmologic AEs will be recorded on the AE eCRF page with a mark for AESI. For additional information on the reporting of AESIs refer to Attachment 2.

Anticipated adverse events may be recorded and reported based on local rules and regulations. A list of events considered anticipated events for the purposes of this study, and their reporting requirements can be found in Attachment 1.

All AEs, regardless of seriousness, severity, or presumed relationship to study drug, must be recorded using medical terminology in the source document and the eCRF. Whenever possible, diagnoses should be given when signs and symptoms are due to a common etiology (eg, cough, runny nose, sneezing, sore throat, and head congestion should be reported as “upper respiratory infection”). Investigators must record in the eCRF their opinion concerning the relationship of the AE to study therapy. All measures required for AE management must be recorded in the source document and reported according to sponsor instructions.

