### **12.3.3. Adverse Events of Special Interest**

The following events are considered to be events of special interest in this study based on nonclinical studies conducted with atabecestat on reported findings for BACE knockout animals or other BACE inhibitors in development.

- Lightening of skin
- Lightening of hair
- Ophthalmologic AEs

All initial reports of treatment-emergent lightening of skin or hair, or treatment-emergent ophthalmologic AEs must be reported to the sponsor by the investigational staff within 24 hours of their knowledge of the event even if these events do not meet the definition of an SAE. For additional information on the reporting of AESIs refer to Attachment 2.

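### SAP 6.1 gives the AESI summary no category for eye events other than retinal changes and iris coloration, although the protocol makes every ophthalmologic AE an AESI

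*SAP*

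**What the plan says.** **Protocol.** The AESI paragraph of section 11.10 sets the categories: "Lightening of hair, lightening of skin, and ophthalmologic adverse events are AESIs". It then says of output: "Subjects with AESIs may be counted or listed". Section 12.3.1 covers data capture: "Adverse events of special interest ie, lightening of skin, lightening of hair and ophthalmologic AEs will be recorded on the AE eCRF page". They are to be flagged there as AESIs. Section 12.3.3 covers reporting: "All initial reports of treatment-emergent lightening of skin or hair, or treatment-emergent ophthalmologic AEs must be reported to the sponsor" within 24 hours, even when the event is not serious. Section 3.2.7 and Attachment 2 use the same three categories. None of these places restricts the eye category by structure, type or severity.

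**SAP.** Section 6.1 makes a firmer commitment on output than the protocol does: "Incidence of other treatment-emergent adverse events of special interest will be summarized". The next sentence gives source and content: "Hypopigmentation related and retinal related adverse events are identified by the investigator on the AE eCRF page and include". Two groups follow:

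- Hypopigmentation related: "Hair and skin hypopigmentation (events related to lighting hair, skin coloration, or iris coloration").
- Retinal related: "Retinal changes".

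The SAP contains no general ophthalmologic category and gives no reason for a narrower set. Section 6.1 also defines a hepatic group by a MedDRA query and adds an open-ended list of further preferred-term clusters. The clusters named as examples are rash, sleep disorder, depression and anxiety; none concerns the eye.

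**The concern.** The SAP should turn the protocol's safety categories into tables. For hair and skin it does. For the eye it substitutes a smaller category, and a reader of the AESI summary would have no way to tell that the denominator of interest had changed from all eye events to retinal ones.

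The eye category was a deliberate choice. The amendment history shows that adding it was the stated purpose of Amendment 2, on a recommendation from a regulatory procedure, and the current protocol text keeps it. Section 1.4 reports that drug distribution is highest in pigmented tissue, eye and skin among others. Section 9.9 names a dermatological examination among the safety assessments but no eye examination, so reported AEs appear to carry most of the information on eye safety. If the AESI summary covers only part of those reports, a between-arm imbalance in the remainder would not show in the place where readers are told to look for it.

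**Working it through.** There is no plan figure to reproduce, and no sample size, error rate or event rate is involved. The check is a mapping of categories.

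**Step 1: map each protocol AESI to the SAP.**

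| Protocol AESI (11.10, 12.3.1, 12.3.3, Attachment 2) | SAP 6.1 category | Covered? |
|---|---|---|
| Lightening of hair | Hypopigmentation related | Yes |
| Lightening of skin | Hypopigmentation related | Yes |
| Ophthalmologic AE: retina | Retinal related | Yes |
| Ophthalmologic AE: iris coloration | Hypopigmentation related | Yes, but grouped with hair and skin |
| Ophthalmologic AE: any other, such as lens, cornea or vision | None named | No |

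**Step 2: state what would be missed.** For one treatment arm, let E be the number of subjects with any treatment-emergent ophthalmologic AE, and let C be the number with at least one retinal or iris-coloration event. Under the SAP's named categories the AESI summary covers C of the E subjects, so

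undercount = E − C,

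which is the number of subjects whose only ophthalmologic AEs are of other types. It is zero if every subject with an eye AE has a retinal or iris event, and positive otherwise. Neither document gives E, C or a rate from which to estimate them, so the difference cannot be given a value.

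**Step 3: check whether the covered part can be recovered.** If hypopigmentation is shown as a single line, iris events are mixed with hair and skin events. Even C could then not be read from the AESI summary.

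**Step 4: check the eCRF source.** Protocol 12.3.1 describes an AESI mark that applies to ophthalmologic AEs in general. SAP 6.1 describes investigator identification of hypopigmentation and retinal events. The eCRF page itself is not in the documents. If the mark covers all eye AEs, the SAP leaves collected information unused. If it offers only a retinal option, the mark alone cannot deliver the protocol's category and coded terms are needed.

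**Step 5: check where the omitted events do appear.** SAP 6.1 includes all reported treatment-emergent AEs, with number and percentage of subjects for each event. The protocol synopsis plans AE incidence by body system and preferred term. SAP 6.1 does not repeat the body-system wording, but nothing in it withdraws that plan. The events are therefore still tabulated.

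**The case against.** The strongest defence is that the SAP's list need not be closed. The AESI commitment is general, the two groups are described by what they include, and the preferred-term clusters are expressly open-ended. On that reading an ophthalmologic summary could still be produced. Protocol 11.10 is only permissive about AESI output, so no analysis promised in the protocol is broken. Expedited reporting by sites does not depend on the SAP. Dosing has stopped, safety is summarised descriptively, and the general AE tables hold every event.

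Much of this stands. It limits the consequence to one descriptive summary. It does not remove the mismatch: the permissive wording concerns output and leaves the definition of the category unchanged, and it was the SAP that chose to say AESI incidence will be summarised. An eye grouping that is possible but unnamed is not prespecified. Stopping the trial early does not explain a narrower eye category, since safety is still to be summarised.

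Four stronger readings are tempting, and the documents do not support them.

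- A reader might infer that retinal changes are the only eye events counted. Iris coloration is counted too, under hypopigmentation.
- A reader might infer that an undercount is certain. It requires other eye events to occur and the SAP list to be applied literally.
- A reader might want to put a percentage on the omission. That would need the share of eye AEs that are retinal, and no document gives it.
- A reader might infer that eye events disappear from safety reporting. They do not, and a body-system row would group them by arm.

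**Conclusion.** The mismatch between the two documents is real and unexplained. The protocol's eye AESI is all ophthalmologic AEs; the SAP's named AESI categories reach only retinal changes and, under another label, iris coloration. Followed as written, the AESI incidence summary would leave out any other treatment-emergent eye AE.

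The size is undetermined and may be zero. The conclusion assumes that the two SAP groups are applied as the full content of the AESI summary, and that at least one subject has eye events of other types only. It affects one descriptive safety summary and no efficacy result. It still merits correction, because the rule as written misstates a safety category that the protocol defines consistently.

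**What to change.** In SAP 6.1, replace the retinal-related group with a group called Ophthalmologic AEs. Define it as all treatment-emergent eye AEs that are either marked as AESI on the AE eCRF page or coded to MedDRA eye-disorder terms. Count each subject once in the group row, and show retinal changes and iris coloration as sub-rows. State whether iris coloration is also kept under hypopigmentation, so that any overlap is visible. Rewrite the sentence on investigator identification so that it matches the AESI mark described in protocol 12.3.1. If the sponsor intends the narrower scope, the SAP should say so and give the reason.

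No extra rule is needed for the two analysis periods, because the opening of SAP section 6 already calls for safety summaries both on and off treatment.

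The cost is a change of SAP wording and one re-specified descriptive table. AEs are already to be coded in MedDRA, so the coded-term part needs no new data; whether the eCRF mark separates eye events cannot be confirmed from the documents. The downside is partial overlap with any body-system row for eye disorders in the general AE tables.
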